3.2. STUDY OUTCOME MEASURES

Primary

Sensitivity, specificity, positive and negative predictive value of digital FCM for detection of clinically significant prostate cancer at surgical margins, with traditional H&E histopathology as the reference standard, on a per-patient basis. Clinically significant cancer is defined as Gleason score >/=7 (ISUP Grade Group >/=2).

Secondary

Sensitivity, specificity, positive and negative predictive value of digital FCM for detection of cancer at surgical margins, with traditional H&E histopathology as the reference standard, on a per-image/margin level.

Area under the receiver operating characteristic curve (AUC) for cancer detection of digital FCM with traditional H&E histopathology as the reference standard.

Agreement of digital FCM with the pathology report for cancer length at margin (mm) on a margin and patient level.

Agreement of digital FCM with the pathology report for cancer grade at margin (mm) on a margin and patient level.

Cohen's kappa coefficient for agreement between readers (two individual histopathologists, histopathologist vs trainee histopathologist, histopathologist vs urologist)

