2. STUDY OBJECTIVES

Primary

To determine the accuracy of digital FCM in detecting and ruling out positive surgical margins in prostate specimens on a patient level, in patients undergoing radical prostatectomy for prostate cancer.

Secondary

To determine the accuracy of digital FCM in detecting and ruling out positive surgical margins on an individual margin/image level.

To evaluate the classification performance of FCM in differentiating between low- and high-grade prostate cancer.

To assess interobserver variability in reporting of digital FCM images.

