7. STATISTICS AND DATA ANALYSIS

7.1. Sample size calculation

The sample size for diagnostic studies incorporating the prevalence of the PSM was calculated based on expected sensitivity of 0.86 and specificity of 0.96 reported by Baas et al⁷. The authors included 49 patients and analysed 96 prostate sides (a per patient analysis was not carried out). The prevalence of a PSM as detected by standard pathology analysis was 15%. The study did not have an a priori sample size estimation and was not blinded.

The sample size for the planned study was calculated to power a sensitivity analysis in line with the practical application of the new test i.e. that detection of a PSM by FCM would be a safe trigger for a change of intra-operative management.

The following assumptions were made:

- Sensitivity 0.85
- Specificity 0.95
- Prevalence of PSM: 30%. The assumption is based upon a review of 768 historical RPs performed at our centre. The over-all PSM rate was 41% due to high admixture of high-risk patients from the local unscreened population, 47% for high-risk cancers, 37% for intermediate risk cancers and 34% for low-risk cancers.
- Precision: +/- 14 points (a variability deemed sufficient for a pilot study)
- Confidence level: 95%
- Expected dropout rate for poor scans: 10%

Estimated sample size for sensitivity is n=27 PSM patients, inflated by 10% to n=30 for expected drop out. Adjusting for the prevalence of 30% a final sample size of 100 patients is deemed sufficient.

Short Title:	Sponsor:	Version:	Date:
IP8-FLUORESCE	ICHNT	1.2	02 April 2024

Since the true prevalence of PSMs for the study cohort is not known, an interim assessment of observed PSM rate is planned a priori. This will be used to adjust the sample size accordingly.

Assessment of the interim PSM rate is planned after 50 patients by a pre-specified independent assessor nominated before the start of the study. The assessment is based on the clinical histopathology reports for each patient which includes PSM status.

Example for sample size adjustment after interim analysis of prevalence are presented as follows: If the observed PSM rate is 25% the sample size would need to be increased to 120 patients. Conversely, if the observed PSM rate is 35% the sample size would decrease to 86 patients.

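### The primary outcome counts only Gleason 7 or higher at the margin, but the primary objective, sample size and interim rule are for any positive margin, so the planned ±14 points is not secured for the primary outcome

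*Protocol*

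**What the plan says.** The primary objective in section 2 is accuracy in "detecting and ruling out positive surgical margins in prostate specimens on a patient level". It sets no grade threshold.

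The primary outcome in 3.2, repeated in the study summary, is per-patient sensitivity, specificity and predictive values of "digital FCM for detection of clinically significant prostate cancer at surgical margins". The same section adds the threshold: "Clinically significant cancer is defined as Gleason score >/=7 (ISUP Grade Group >/=2").

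The sizing in 7.1 is for PSM without a grade threshold:

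- The sensitivity comes from an earlier study of PSM detection, rounded to 0.85.
- The prevalence line reads "Prevalence of PSM: 30%. The assumption is based upon a review of 768 historical RPs performed at our centre". The historical rate quoted beside it is 41% overall and 34% even in low-risk cancers.
- The target is 27 PSM patients, raised to 30 for poor scans, which gives N = 100.
- N is re-set after 50 patients from the observed PSM rate. On the source of that rate: "The assessment is based on the clinical histopathology reports for each patient which includes PSM status".

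Table 1 in 3.1 records margin status (negative, positive, indeterminate) separately from highest grade (3, 4 or 5), for each margin and overall.

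**The concern.** Any PSM and Gleason 7 or higher at the margin are different target conditions. A patient whose only margin cancer is grade 3 is positive for the objective, counts towards the 27, and counts at the interim, yet is disease-negative for the primary outcome. Table 1 has a place for exactly this patient.

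Two things are at stake. First, it is unclear what the main result estimates. The secondary accuracy outcome drops the grade threshold but is per image or margin, and the AUC outcome states no unit of analysis. Second, the denominator for the primary sensitivity may be smaller than planned, and the interim rule adjusts N on an event that is not the primary event.

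**Working it through.** **Inputs from 7.1.** Sensitivity 0.85, 95% confidence (z = 1.96), precision ±0.14, 10% poor scans, PSM prevalence 30%, historical PSM rate 41%.

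**The protocol's own figures.** For the precision of one proportion, n = z² p(1−p)/d² = 1.96² × 0.85 × 0.15 / 0.14² = 24.99, so 25. The protocol states 27, which corresponds to ±13.5 points; the difference is minor. From 27 the chain reproduces:

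- 27/0.90 = 30
- 30/0.30 = 100
- 30/0.25 = 120
- 30/0.35 = 85.7, so 86

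The interim rule is therefore N = 30 / observed PSM rate. All of this is for any PSM.

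**Precision for the stated primary outcome.** Let f be the share of PSM patients with Gleason 7 or higher at the margin. The documents do not give f, so a range is shown. At N = 100, evaluable positives = 100 × 0.30 × 0.90 × f = 27f, and the half-width is 1.96 × √(0.1275 / 27f). The last column keeps the protocol's 30 reference-positives: N = 30/(0.30f).

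| f | Evaluable positives | Half-width (points) | N needed |
|---|---|---|---|
| 1.0 | 27.0 | 13.5 | 100 |
| 0.9 | 24.3 | 14.2 | 112 |
| 0.8 | 21.6 | 15.1 | 125 |
| 0.7 | 18.9 | 16.1 | 143 |
| 0.5 | 13.5 | 19.0 | 200 |

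±14 needs 25 positives, so f must be at least 25/27 = 0.93.

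**The interim rule.** Because N = 30 / PSM rate, the rule aims at about 27 evaluable any-PSM patients whatever the rate. It does not respond to f. Suppose the PSM rate is the historical 41%. With N kept at 100 there would be 36.9f evaluable positives, and f of 25/36.9 = 0.68 would suffice. The rule would instead cut N to 30/0.41 = 73.2, so 74, and the required f returns to about 0.93.

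A simulation used a true PSM rate of 41%, an interim at 50 patients, N = 30 / observed rate with a floor of 50, and 90% readable scans. Median N was 75. The chance of at least 25 evaluable Gleason 7 or higher positives was:

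| f | Chance |
|---|---|
| 1.0 | 87% |
| 0.9 | 55% |
| 0.8 | 25% |
| 0.7 | 8% |

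**The case against.** - **The shortfall is conditional.** A reader might infer that ±14 is definitely missed. The documents do not support that, because f is not given. At f = 0.9 the half-width is 14.2, practically the stated value. The protocol calls ±14 adequate for a pilot study and sets no hypothesis test or success threshold. This stands: a loss of one or two points would not by itself make the matter serious. The weight rests on the contradiction over the target condition, which does not depend on f.
- **The 30% might already be 41% discounted for grade** (30/41 = 0.73). The protocol labels it PSM prevalence and gives no such reason, and the interim still counts any PSM.
- **Clinically significant might refer to the whole-gland grade**, which would narrow the gap. The outcome wording places the cancer at the margin, and Table 1 grades each margin.
- **Under-grading.** A reader might infer that finding margin cancer on FCM but grading it too low is a false negative. The protocol does not define FCM-positive for the primary outcome. FCM margin status judged against a Gleason 7 or higher reference is an equally possible reading. Only if FCM-positive also requires FCM grade 7 or higher would under-grading add misses.
- **The interim figures extrapolate.** The protocol works the rule only at 25% and 35%; 41% is a natural extension but not stated. The 8% at f = 0.7 is the lowest of the four values shown and should not be quoted alone.
- **An unseen statistical analysis plan might reconcile the terms.** The primary outcome, sample size and interim rule are fixed in the protocol and conflict there.

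**Conclusion.** The mismatch is on the face of the protocol. The primary outcome has one target condition; the primary objective, the prevalence, the sample size and the interim rule have another, and nothing in the document reconciles them. Per-patient sensitivity and specificity for any PSM, which the primary objective asks for, is not explicitly listed as an outcome.

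The planned precision is not secured for the primary outcome. It holds at N = 100 and 30% PSM only if f is about 0.93 or more, and the half-width widens to 16.1 points at f = 0.7 and 19.0 at f = 0.5. The interim rule cannot make up a shortfall, and at a high PSM rate it removes the slack that might have covered one. These sizes rest on the assumed f, on the protocol's 0.85 carrying over to the graded target, and on 10% poor scans. The documents require one consistent target condition; they do not settle which it should be.

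**What to change.** Use one target condition throughout, chosen before any image is read. Two options are open:

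- **(a) Any PSM as the per-patient primary outcome**, with Gleason 7 or higher at the margin as secondary. This matches the objective, sizing and interim rule as they stand. The cost is wording in the study summary and 3.2; Table 1 already records both status and grade, so no patients or data are added.
- **(b) Gleason 7 or higher at the margin stays primary.** Align the objective, state the assumed prevalence of this condition, restate the precision for N = 100, and base the interim on the rate of Gleason 7 or higher at the margin. This requires the clinical reports to give grade at the margin; 7.1 says only that they include PSM status, so extra data may be needed. Keeping the planned 30 reference-positives would take N from 112 (f = 0.9) to 200 (f = 0.5).

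Under (b), also state whether FCM-positive requires the FCM grade to meet the threshold. Images are read only after recruitment is complete, so either change can be made without knowledge of the accuracy results.

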The specimen will then be formalin-fixed and paraffin-embedded before undergoing formal histological assessment for margin status by a histopathologist. Clinical management of these patients will follow current standard-of-care pathways.

Outcome reporting

The histopathology slides for each patient will be digitally scanned and uploaded to a secure cloud-based server alongside the FCM images. All files will be pseudoanonymised and the server locked until the recruitment target has been reached. Once recruitment is complete, histopathology slides will be re-reported by expert independent uro-pathologists who will also report the margin status for the FCM images. They will be blinded to the margin status and the patient details in the histology report when making the FCM report, and vice versa. The histopathologist will provide the overall margin status on a per-patient level, as well as a report on a margin level, for length of cancer at the margin and highest grade (Table 1).

Table 1. Example case report form for margin status for a single patient.

	FCM Margin Status			Histopathology Margin Status		
	(0=negative, 1=positive, 2=indeterminate)	Length (mm)	Grade (highest; 3, 4, 5)	(0=negative, 1=positive, 2=indeterminate)	Length (mm)	Grade (highest; 3, 4, 5)
Base						
Apex						
Lateral (left)						
Lateral (right)						
Anterior						
Posterior						
Overall						

The recruitment target is 5 patients for the pilot phase, followed by 100 patients for the main phase. The study will run for 6 months or until the recruitment target is reached.

Short Title:	Sponsor:	Version:	Date:
IP8-FLUORESCE	ICHNT	1.2	02 April 2024

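### The protocol lists an AUC, but the FCM reads it describes include no graded suspicion score, so the AUC would add little to sensitivity and specificity

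*Protocol*

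**What the plan says.** Section 3.2 of the Protocol, and the Study Summary in the same terms, lists this secondary outcome: "Area under the receiver operating characteristic curve (AUC) for cancer detection of digital FCM", judged against H&E histopathology. It does not name the FCM score whose threshold is varied, or say whether the curve is per patient or per margin.

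The Outcome reporting part of section 3.1 describes what the readers record. They give an overall margin status per patient, "as well as a report on a margin level, for length of cancer at the margin and highest grade". Table 1, captioned "Example case report form for margin status for a single patient", codes status as "0=negative, 1=positive, 2=indeterminate" and has columns for length (mm) and highest grade (3, 4, 5). The columns are the same for FCM and for histopathology, with one row per margin and one overall. No suspicion or confidence rating is described anywhere in the Protocol.

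Files stay on a locked server until the recruitment target is reached, and only then are the FCM images read. Section 7 leaves full analysis details to a statistical analysis plan, which is not at hand.

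**The concern.** An ROC curve shows how sensitivity and specificity trade off as the threshold on an ordered score moves. A yes/no call has only one threshold. Its curve is two straight lines through one point, and the area under it is a fixed function of sensitivity and specificity, both of which are already listed as outcomes.

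The other recorded fields do not fill this gap well. Length and grade describe cancer that the reader has seen. They give no ranking among reads called negative, where missed positive margins would lie, and ruling out positive margins is part of the primary objective in section 2. Length also measures extent rather than certainty, and it has its own agreement outcome.

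The risk is that a listed outcome is reported as if it were separate evidence of discrimination when it restates two other results. A statistical analysis plan can define how a recorded score is analysed, but it cannot supply a score that no reader was asked to give.

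**Working it through.** **Inputs.** Section 7.1 gives "Sensitivity 0.85" (Se), "Specificity 0.95" (Sp) and a positive-margin prevalence of 30%. The indeterminate rate u is not in the Protocol. It is assumed here at 5%, 10% and 20%, equal in margin-positive and margin-negative cases. The 10% in section 7.1 is dropout for poor scans, not an indeterminate rate.

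**The plan's own figure.** The Protocol states no AUC value and no AUC precision, so there is none to reproduce. Its sample size is built on sensitivity alone ("Precision: +/- 14 points").

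**Definition.** AUC = P(score in a case > score in a non-case) + ½ P(tie).

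**1. Yes/no status.**
- Case ranked higher: Se × Sp = 0.85 × 0.95 = 0.8075.
- Ties: Se(1 − Sp) + (1 − Se)Sp = 0.0425 + 0.1425 = 0.185, half of which is 0.0925.
- AUC = 0.8075 + 0.0925 = 0.90 = (0.85 + 0.95)/2.

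At the 0.86 and 0.96 that section 7.1 cites from the earlier margin study, it is 0.91.

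**2. Three statuses, ordered negative < indeterminate < positive.** Se and Sp apply to the determinate reads. The four combinations give

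AUC = 0.90(1 − u)² + u(1 − u)(Se + Sp) + 0.5u² = 0.90 − 0.40u².

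| Assumed u | AUC |
|---|---|
| 5% | 0.899 |
| 10% | 0.896 |
| 20% | 0.884 |

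Dropping the equal-rate assumption changes little. Rates of 5% in cases and 15% in non-cases give 0.892, 15% and 5% give 0.902, and 0% and 10% give 0.895.

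**3. FCM length as the score.** Set length to 0 for every FCM-negative read, and assume no indeterminate reads. Only pairs of a true positive and a false positive are re-ranked by length; their share is Se(1 − Sp) = 0.0425.
- Every false positive longer than every true positive: 0.85 × 0.95 + 0.15 × 0.95 × 0.5 = 0.87875.
- Every false positive shorter: 0.85 + 0.15 × 0.95 × 0.5 = 0.92125.

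The AUC therefore lies within 0.90 ± 0.021, whatever the lengths are.

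**4. Why so little moves.** The expected share of FCM-negative patients is 0.15 × 0.30 + 0.95 × 0.70 = 0.71. Under a length score these 71% are tied at the bottom. The curve from (1 − Sp, Se) = (0.05, 0.85) to (1, 1) is then a straight line by construction.

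**5. Entry codes used as ranks (hypothetical).** With 0 < 1 < 2 taken literally, indeterminate outranks positive, and AUC = 0.90(1 − u)² + u(1 − u) + 0.5u². This is 0.861, 0.824 and 0.756 at u = 5%, 10% and 20%.

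**The case against.** Four arguments count against the point.

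- **The AUC can be calculated.** This stands. Three ordered statuses give two cut-points and a valid ordinal curve, and length gives thresholds among positive reads. A reader might infer that the outcome cannot be estimated at all; the documents do not support that. What remains is that the result is nearly fixed by sensitivity and specificity.
- **The codes are entry labels.** This also stands. A reader might infer from the coding that indeterminate will be ranked above positive and the AUC pulled down to 0.824. The Protocol nowhere plans to use the codes as a score, the same labels serve the histopathology columns, and the figure rests on an assumed 10% indeterminate rate. The coding deserves a caution and is not an error in the plan.
- **The form is an example, and the images are kept.** The final form may differ. A reader might infer that a missing score could never be recovered once reading is done, but stored digital images could be read again under blinding. That would cost a second round of reads, whereas a field added beforehand costs almost nothing.
- **The definition belongs in the statistical analysis plan.** This holds for choosing the score, the level of analysis and the handling of indeterminate reads. It does not hold for collecting the score, and the Protocol's account of what readers report contains none.

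**Conclusion.** The listed outcome and the described data collection do not match. At the planning values the AUC is 0.90 from a yes/no status, 0.884 to 0.899 from three ordered statuses at equal assumed indeterminate rates of 5% to 20%, and 0.879 to 0.921 from length. None of these tells the reader much beyond sensitivity and specificity.

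The conclusion assumes that the final form follows Table 1 and that FCM-negative reads carry no graded information. The figures assume the planned sensitivity and specificity. The length band has half-width Se(1 − Sp)/2, so it would widen if specificity fell below plan, although negative reads would still be tied.

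The consequence is limited. The AUC is one of several secondary outcomes, and neither the primary outcome nor the sample size uses it. It is still worth correcting now, because the change is easiest before the images are read.

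**What to change.** Before image reading starts, add one field to the FCM part of Table 1, for each margin and overall: a 5-point suspicion score for cancer at the margin, from 1 (definitely absent) to 5 (definitely present). Name this score in section 3.2 as the basis of the AUC, and state whether the curve is per patient, per margin or both. If no score is to be collected, delete the AUC outcome.

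If status is ever used as an ordinal score, place indeterminate between negative and positive and do not use the codes 0/1/2 as ranks. This needs only a mapping at analysis, not a change to the form.

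The cost is one extra field and a few seconds per image, with no additional reader and no change to recruitment.

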4. PARTICIPANT ENTRY

4.1. PRE-REGISTRATION EVALUATIONS

All participants scheduled for RP undergo routine history taking, examination, diagnostic workup, and staging to ensure suitability for the procedure. All patients will undergo standard of care preoperative workup including renal and liver function testing, ECG, and anaesthetic review.

Due to the ex vivo design of the study, no screening visits are required. Further, patients will not have any contact, undergo any tests, or require any follow-up out of line with standard of care management other than the digital FCM scan intraoperatively.

Short Title:	Sponsor:	Version:	Date:
IP8-FLUORESCE	ICHNT	1.2	02 April 2024

4.2. INCLUSION CRITERIA

Any person over the age of 18 with a prostate undergoing radical prostatectomy at Imperial College Healthcare NHS Trust during the study period.

All nerve sparing and non-nerve sparing cases will be included consecutively.

4.3. EXCLUSION CRITERIA

Subjects who are unwilling or unable to consent for ex vivo tissue research through Imperial College Healthcare Tissue Bank (ICHTB).

Subjects scheduled for salvage RARP

Subjects enrolled in concurrent clinical trials requiring ex vivo prostatic tissue for research.

4.4. WITHDRAWAL CRITERIA

Patients may decide to opt out of IP8-FLUORESCE at any time. This is entirely within their right to do so. Such cases will be reported to the research team so that no further data are entered onto the database. Data captured before consent was withdrawn will be used in the study, but no further data, beyond this date will be collected or used in any analysis. Reason for withdrawal must be recorded in the CRF/eCRF and medical records. We will continue to recruit patients until the target number for study is met.

5. ADVERSE EVENTS

5.1. **DEFINITIONS**

Adverse Event (AE): any untoward medical occurrence in a patient or clinical study subject.

Serious Adverse Event (SAE): any untoward medical occurrence or effect that:

- Results in death
- Is life-threatening refers to an event in which the subject was at risk of death at the time of the event; it does not refer to an event which hypothetically might have caused death if it were more severe
- Requires hospitalisation, or prolongation of existing inpatients' hospitalisation
- Results in persistent or significant disability or incapacity
- Is a congenital anomaly or birth defect

Short Title:	Sponsor:	Version:	Date:
IP8-FLUORESCE	ICHNT	1.2	02 April 2024

Medical judgement should be exercised in deciding whether an AE is serious in other situations. Important AEs that are not immediately life-threatening or do not result in death or hospitalisation but may jeopardise the subject or may require intervention to prevent one of the other outcomes listed in the definition above, should also be considered serious.

